7.2 Recording Adverse Events and Adverse Reactions (AEs and ARs)

All AEs and ARs will be recorded from the date of randomisation until completion of 12-month visit or until the participant withdraws. Participants will be asked about AEs and ARs at each scheduled study visit.

All AEs and ARs (unless listed below in 7.3) will be recorded in the participants' medical notes and the data entered onto the AE page in the electronic case report form (eCRF). The local site PI's clinical judgement should be used to determine if an AE is reportable as an AR.

7.3 Exclusions to Adverse Event (AE) reporting

Due to the nature of the study design the following AEs are exempt from recording unless the PI deems them to be related or serious;

- Falls -these are captured as an outcome. However, any injury resulting from a fall will be recorded as an Adverse Event.
- The following symptoms are routinely experienced in people with OH and therefore will not be reported as AEs:
 - Dizziness/light-headedness/vertigo
 - Postural induced visual disturbance
 - Weakness/fatigue/tiredness
 - Difficulty concentrating
 - Headache or head/shoulder/neck discomfort
 - Tremulousness
 - Pallor
 - Anxiety
 - Palpitations
 - Nausea

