5.3.1 Masking

This is an open-label, unblinded trial. Study participants, clinicians and the NCTU team will be aware of treatment allocation. The Statistical Analysis Plan (SAP) will be developed by statisticians who are unaware of treatment allocation and will be finalised and signed-off prior to the first DMC meeting that reviews unblinded data. The SAP will contain full details of both the interim and final analyses, with details of who will perform these analyses. Trial statisticians will have access to unblinded data for the purposes of creating DMC reports and conducting the interim analysis. No other members of the research team will have access to the unblinded data contained in closed DMC reports, unless the DMC request that unblinded information is released. In the case that an amendment is proposed to the SAP, this will be approved by an appropriate blinded independent statistician (the independent Trial Steering Committee statistician or an appropriate senior member of the Biostatistics Research Group).

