7.4.3 Assessment of Causality

All AEs/ARs occurring from the time the participant is randomised into the study until the participant's 12-month study visit or participant withdraws, must be assessed for the relationship to the study intervention by the PI/delegated clinician. Due to the low risk nature of the study intervention, any AE classified as 'unrelated' or 'unlikely to be related' will be deemed unrelated for the purpose of reporting SUSARs. If there is any doubt, the CI may be consulted. If the PI and CI assessment differ then both assessments will be reported. The following definitions should be used:

Unrelated	The event is not considered related to the study interventions.	Unrelated
Unlikely to be related	There is little evidence that the trial intervention caused the event. There is another more likely explanation.	
Possibly related	There is some evidence that the trial intervention may have caused the event. Other causal factors cannot be ruled out.	Related
Probably related	The temporal relationship and an absence of a more likely explanation suggest that the study intervention is the most likely cause.	

Definitely related	The known effects of the study intervention indicate that it is the most likely cause; other contributing factors can be ruled out.	
--------------------	---	--

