2.4 Definition of outcome measures

2.4.1 Primary endpoint

The Orthostatic Hypotension Questionnaire (OHQ) [1] is completed at baseline, three, six and 12 month follow-up. The primary endpoint is the overall composite OHQ score at six months. The OHQ is validated for use in both clinical and research settings [2] and will be scored according to the validated scoring method [1].

The OHQ is composed of two sections: the first section consists of six questions, which rate the severity of six different symptoms on a scale of 0 to 10 (Orthostatic Hypotension Symptom Assessment Scale – OHSAS). The second section is composed of four questions, which rate the impact of symptoms on standing and walking (Orthostatic Hypotension Daily Activity Scale – OHDAS). The questions on the OHDAS are scored on a scale of 0 to 10 but also include an option of 'cannot be done for other reasons'.

The OHSAS score is calculated by averaging the responses to the six questions on the OHSAS. Similarly, the OHDAS score is calculated by averaging responses to the four questions on the OHDAS. Items which are scored as zero or answered 'cannot be done for other reasons' at baseline are not included in the scoring. Post-baseline scores are calculated using only those items which were included in the baseline score. If any item on the OHDAS which was included in the baseline score is missing or answered 'cannot do for other reasons' at a post-baseline assessment a value will be assigned using last observation carried forward.

An overall composite OHQ score will be calculated by averaging the OHSAS score and the OHDAS score. This score takes a value between 0-10, with higher scores indicating worse symptoms / interference.

At each follow-up time point the change from baseline will also be calculated as the follow-up score minus the baseline score.

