6. SAFETY

6.1 Adverse Events

Safety data will be reported in the Safety Analysis Set, with adverse events reported according to treatment received at the time of AE onset.

The following metrics will be used to provide an overall summary of adverse events reported while exposed to each treatment group, see Example Table 10:

- The number of participants exposed to each treatment group.
- The total exposure time (measured in years) to each treatment group, i.e. a sum across all participants of the amount of time they were exposed to each treatment group.
- Number and proportion of participants affected by at least one adverse event while exposed to each treatment group. Percentages will be calculated out of those exposed.
- Worst grade (mild, moderate, severe) adverse event reported while exposed to each treatment group. This will be tabulated with percentages calculated out of those exposed.
- Total number of adverse event occurrences reported by each participant while exposed to each treatment group. This will be tabulated (with percentages calculated out of those exposed) and/or reported as median and range, as appropriate
- Total number of unique adverse event occurrences (i.e. different preferred terms) reported by each participant while exposed to each treatment group. This will be tabulated (with percentages calculated out of those exposed) and/or reported as median and range, as appropriate
- Total number of adverse event occurrences reported across all participants while exposed to each treatment group. This will also be broken down by severity (mild, moderate, severe).
- The incidence rate (IR) of adverse event occurrence while exposed to each treatment group (i.e. total number of AE occurrences / total exposure time).

For each adverse event, at the preferred term level, we will also report the following metrics by treatment group, see Example Table 11:

- The number and proportion of participants experiencing the adverse event at any point while exposed to each treatment group. Percentages will be calculated out of those exposed.
- The worst reported severity (mild, moderate, severe) for the adverse event at any point while exposed to each treatment group. Percentages will be calculated out of those exposed.
- The total number of occurrences of the adverse event while exposed to each treatment group.
- The total number of occurrences of the adverse event, by severity (mild, moderate, severe), while exposed to each treatment group.

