This data may also be presented graphically as dot plots of the proportion of participants affected by each adverse event. The number of participants affected and the total number of occurrences will be shown on the graph. See Example Figure 5. Had the trial continued to full enrolment the graph would have also shown a measure of relative risk with 95% CIs, with separate graphs produced for the comparison of fludrocortisone and control, midodrine and control, and fludrocortisone and midodrine. If there are many different adverse events reported we will focus on the graphical presentation of only those occurring in a specified proportion of participants (e.g. >3% participants in either group).

The same summaries will also be reported for adverse reactions (adverse events reported as possibly, probably or definitely related to trial treatment) and for non-serious events (as required for EudraCT reporting).

Adverse events which resulted in treatment discontinuation will also be tabulated. Percentages will be calculated out of those exposed to each treatment group.

Example Table 10: Summary of adverse events

	Control	Fludrocortisone	Midodrine
Number of participants exposed; N			
Total exposure time (years); N			
Number of AEs per			
participant; N (%)			
0			
1-3			
4-6			
>6			
Median (IQR); Range			
Number of unique AEs per			
participant; N (%)			
0			
1-3			
4-6			
>6			
Median (IQR); Range			
Worst grade reported across all AEs; N (%)			
Mild			
Moderate			
Severe			
Total number of AEs			
reported; N			
Mild			
Moderate			
Severe			
Incidence of AEs; IR (95% CI)			

		Number	(%) of participants	affected ^{1,2}	Number of occurrences ¹			
Adverse event term		Control	Fludrocortisone	Midodrine	Control	Fludrocortisone	Midodrine	
		N =	N =	N =	N =	N =	N =	
	Overall							
Nausaa	Mild							
Nausea	Moderate							
	Severe							
	Overall							
Usadasha	Mild							
Headache	Moderate							
	Severe							
	Overall							
AE 1	Mild							
AEI	Moderate							
	Severe							
	Overall							
AE 2	Mild							
AE Z	Moderate							
	Severe							

Example Table 11: Summary of adverse events by type

¹While exposed to each treatment group

 2 % calculated out of total number exposed. If >1 occurrence per participant the worst reported severity is tabulated

Example Figure 5: Proportion of participants affected by each AE

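### Ten symptom groups enter the adverse-event data only if an unblinded investigator calls them related or serious, so the by-arm AE tables are expected to be biased for those terms and the totals that include them

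*Protocol*

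**What the plan says.** - **Recording rule.** Protocol 7.3 states that "the following AEs are exempt from recording unless the PI deems them to be related or serious". Apart from falls, which are also counted from participant diaries, it lists ten symptom groups: dizziness, visual disturbance, weakness or fatigue, poor concentration, headache ("Headache or head/shoulder/neck discomfort"), tremulousness, pallor, anxiety, palpitations and nausea. The reason given is that they are "routinely experienced in people with OH and therefore will not be reported as AEs".
- **Who applies it.** Protocol 7.4.3 says that events "must be assessed for the relationship to the study intervention by the PI/delegated clinician". Protocol 5.3.1 says: "Study participants, clinicians and the NCTU team will be aware of treatment allocation".
- **What related refers to.** Protocol 7.1 defines an adverse reaction as a response to an investigational product. Protocol 6.2 classes only fludrocortisone and midodrine as such.
- **How events are elicited.** SAP 2.4.2 relies on open-ended questions at visits, with no symptom checklist.
- **What is tabulated.** SAP 6.1 groups events by treatment received at onset. Its list includes "Number and proportion of participants affected by at least one adverse event while exposed to each treatment group", worst grade, number of occurrences, an incidence rate and every preferred term. The shell "Example Table 11: Summary of adverse events by type" has a control column, and its only two named terms are nausea and headache. The same summaries are planned for adverse reactions and for non-serious events, the latter for EudraCT. SAP 6.1 does not mention the Protocol 7.3 rule.

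**The concern.** For most AE terms an event is recorded whatever its cause. For these ten groups a non-serious event is recorded only after a positive causality judgement, made by someone who knows the treatment. On a drug, a rating of possibly related is enough. On conservative management there is no investigational product to blame, so the same symptom has a much narrower route into the data. The table would then set columns side by side that were filled under different effective rules.

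The non-serious summary is the most exposed. For these terms every entry in it must have passed the relatedness test, so it is an adverse-reaction table under an AE label.

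Side effects by strategy are a stated secondary objective (SAP 1.2.2), and Protocol 1.2 says it is unknown whether the drugs' benefits outweigh their harms. Nothing in the planned tables tells a reader that these rows, or the totals containing them, depend on an arm-dependent filter.

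**Working it through.** The plan gives no figure for this point, so there is nothing to reproduce. The recording rule can be written down and its effect calculated on assumed inputs.

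**Inputs, all assumed.** For one listed symptom:
- p = true share of participants with the symptom
- a = share of drug-arm cases judged related
- c = share of control cases judged related
- s = share serious, taken as independent of attribution

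The planned 122 per arm (Protocol 8.3) is used only to turn shares into counts. The trial closed during the pilot, so actual counts will be far smaller. Differences and ratios do not depend on it.

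**Formulas.** A case is recorded if related or serious:
- drug arm: p × (a + s − a·s)
- control: p × (c + s − c·s)

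With equal true p and c = 0:
- recorded difference = p·a·(1 − s)
- recorded ratio = (a + s − a·s)/s, which does not involve p

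**Equal true rates, p = 40%, s = 1%, c = 0.** About 122 × 0.40 = 48.8 participants per arm have the symptom.

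| a | Recorded, control | Recorded, drug | Difference | Ratio |
|---|---|---|---|---|
| 10% | 48.8 × 0.01 = 0.5 | 48.8 × 0.109 = 5.3 | 0.40 × 0.10 × 0.99 = 4.0 points | 0.109/0.01 = 10.9 |
| 25% | 0.5 | 48.8 × 0.2575 = 12.6 | 0.40 × 0.25 × 0.99 = 9.9 points | 0.2575/0.01 = 25.8 |

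Over p = 20-60%, a = 5-50% and s = 1-2%, still with c = 0, the difference runs from 1.0 to 29.7 points and the ratio from 3.5 to 50.5.

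**Some attribution in control.** With c = 1-5%, a = 10-50% and s = 1%, the ratio runs from 0.109/0.0595 = 1.8 to 0.505/0.0199 = 25.4. It equals 1 only when a = c.

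**Unequal true rates, s = 1%, c = 0, a = 10% to 50%.**
- The drug lowers the symptom from 50% to 30% (true difference −20 points). Recorded: 0.30 × 0.109 − 0.50 × 0.01 = +2.8 points, up to +14.6 points. The sign is reversed.
- The drug raises it from 10% to 30% (true difference +20 points). Recorded: 0.30 × 0.109 − 0.10 × 0.01 = +3.2 points, up to +15.0 points. The absolute excess is understated, because drug-arm cases judged unrelated are also dropped, although the ratio is inflated.

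**The case against.** **Direction.** A reader might infer that the rule is bound to create a drug-arm excess. The documents do not support that. Protocol 7.4.3 judges causality against the study intervention, and Protocol section 6 lists conservative management as one of three interventions. It can include salt and fluid loading and compression, so a control symptom can be called related. This stands: the direction is expected, not forced. Only equal attribution removes the bias.

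**Consequence.** Under SAP 3.3 no statistical tests will be done. SAP 6.1 has dropped relative risks from the AE graph, and the graph itself is optional. This also stands. The harm is misleading descriptive counts, including those prepared for EudraCT, and not a false claim of significance. A reader might call safety the main usable output of the closed trial, but neither document says so.

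**Existing safeguards.** Adverse reactions get their own summary, so part of the attribution is visible, and the table with nausea and headache is only a shell. That helps an alert reader. It does not correct the all-AE rows or totals, and it does not disclose the rule.

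**The OHQ.** A reader might infer that an unrecorded symptom is lost from efficacy reporting too, because "Post-baseline scores are calculated using only those items which were included in the baseline score" and items scored zero at baseline are left out. That holds only if the symptom is an OHQ item. The documents say the scale rates six symptoms and never name them, and six items cannot match ten groups one to one.

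**Serious events.** A reader might extend the point to the split between reportable and non-reportable SAEs in Protocol 7.7. SAP 6.2 limits only the chronological listing to reportable events, gives SAE counts by treatment, and also summarises the non-reportable ones. Little is left there.

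**Conclusion.** The point holds as a bias in comparison. The filter, the unblinded judgement and the by-arm tables without separate handling are all in the documents. Together they make the drug-control contrast for the ten groups, and for any total, worst grade or rate that includes them, unreliable as a measure of how often the symptoms occurred.

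This rests on one assumption: that investigators accept relatedness more often for a drug than for conservative management. The assumption is plausible, but the documents do not establish it. The figures above show how the mechanism works and are not estimates. A reader might infer that the tables will simply exaggerate harm. If a drug does cause a symptom, the recorded absolute excess can be smaller than the true one.

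It is worth correcting because the change is cheap, but it does not threaten the trial's conclusions, since no inference is planned.

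**What to change.** In SAP 6.1:

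1. Put the Protocol 7.3 symptom terms in a separate by-arm table with two blocks: serious events whatever the causality, and non-serious events judged related. Add a footnote that non-serious, unrelated occurrences were not recorded in any arm. Keeping the serious block matters, because an adverse-reaction table alone would lose serious events judged unrelated.
2. Give the by-arm AE totals, worst grade, incidence rates, dot plot and non-serious (EudraCT) summary without the non-serious Protocol 7.3 terms. Show the all-recorded totals alongside, so that no reaction is hidden.
3. Where an OHQ symptom item matches a listed term, tabulate by arm the participants newly symptomatic or worse than baseline on that item, including items scored zero at baseline. The OHQ is collected in every arm at every visit and does not pass through the relatedness filter, although it is answered with knowledge of treatment. Terms with no matching item cannot be recovered this way.

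The cost is a few extra table rows, one footnote and slightly smaller totals in the restricted tables. No new data are needed.

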7.4 Assessment of Adverse Events/ Adverse Reactions (AEs/ARs)

AEs/ARs will be recorded at study visits by the research team. AEs/ARs will be recorded on the paper AE log, transcribed into the eCRF and in the patient medical notes. Each AE/AR must be assessed for severity (7.4.1), seriousness (7.4.2) and causality (7.4.3).

7.4.1 Assessment of Severity

Each AE/AR must be assessed for severity by the PI/delegated clinician. The following definitions should be used:

Intensity	Description
Mild	An event tolerated by the patient, causing minimal discomfort and not interfering with everyday activities
Moderate	An event sufficiently discomforting to interfere with normal everyday activities
Severe	An event that prevents normal everyday activities

7.4.2 Assessment of Seriousness

The PI/delegated clinician must make an assessment against the standard definition in the Safety Reporting Definitions (Section 7.1).

7.4.3 Assessment of Causality

All AEs/ARs occurring from the time the participant is randomised into the study until the participant's 12-month study visit or participant withdraws, must be assessed for the relationship to the study intervention by the PI/delegated clinician. Due to the low risk nature of the study intervention, any AE classified as 'unrelated' or 'unlikely to be related' will be deemed unrelated for the purpose of reporting SUSARs. If there is any doubt, the CI may be consulted. If the PI and CI assessment differ then both assessments will be reported. The following definitions should be used:

Unrelated	The event is not considered related to the study interventions.	Unrelated
Unlikely to be related	There is little evidence that the trial intervention caused the event. There is another more likely explanation.	
Possibly related	There is some evidence that the trial intervention may have caused the event. Other causal factors cannot be ruled out.	Related
Probably related	The temporal relationship and an absence of a more likely explanation suggest that the study intervention is the most likely cause.	

Definitely related	The known effects of the study intervention indicate that it is the most likely cause; other contributing factors can be ruled out.	
--------------------	---	--

7.5 Reporting of Serious Adverse Events and Serious Adverse Reactions (SAEs and SARs)

All Adverse Events and Adverse Reactions occurring from point of randomisation until the participants' final study visit that meet the definition of serious (as outlined in Section 7.4.1 above) will be regarded as a Serious Adverse Event or Serious Adverse Reaction. These will need to be reported to NCTU as part of this trial and recorded in the eCRF and patient medical records. All corresponding AEs will be recorded on the eCRF and marked as serious. SAEs must be followed up until resolved.

All SAEs and SARs not listed in Section 7.7, will be reported to the CI, NCTU and Sponsor as soon as possible within a maximum of 24 hours of the site becoming aware of the event.

The initial SAE or SAR report will be made by the site PI (or delegate) completing the CONFORM-OH SAE reporting form. This can be sent by email to [contact] which is automatically distributed to the Senior Trial Manager, Trial Manager, Clinical Trials Assistant, NCTU QA, CI and nominated Sponsor contact. For sites that do not have nhs.net accounts, another secure method may be used but this must be discussed with and agreed by the NCTU Trial Manager(s) prior to use. The initial report can, if necessary, be made to the Clinical Trials Unit by telephone or e-mail and followed up formally using the SAE reporting form.

For each immediately reportable SAE the following information will be collected:

- Full details in medical terms and case description
- Event duration (start and end dates, if applicable)
- Action taken
- Outcome
- Seriousness criteria
- Causality in the opinion of the investigator
- Whether the event is considered expected or unexpected in accordance with the approved RSI if a causal relationship is suspected with study medication

A copy of the completed SAE reporting form will be filed in the ISF as well as in the patient's medical records.

Any change of condition or additional follow-up information should be submitted to NCTU as soon as it is available or at least within 24 hours of the information becoming available. The CONFORM-OH SAE follow-up form should be used for this. Events will be followed up until the event has resolved or a final outcome has been reached.

NCTU contact details:

When reporting SAEs/SARs/SUSARs please send the completed and signed SAE reporting form(s) to the following from a secure nhs.net email address:

Email: [contact]

FAO CONFORM-OH TRIAL MANAGER

A participant should not be withdrawn if they experience an SAE. However, if a participant is withdrawn from the study, the site team will continue to follow up the event until the SAE has resolved or stabilised.

